## **10. MEASUREMENT OF RESPONSE**

Response will be evaluated after 8 weeks of systemic therapy and then every 8 weeks thereafter. The purpose of the 4 week scans is to determine safety. If symptoms develop or clinical deterioration occurs, patients may be imaged prior to the pre-specified time points for imaging. All responses must be confirmed by repeat imaging at least 4 weeks following initial documentation of objective response.

### **10.1 Brain Metastases Response Assessment**

RECIST criteria v1.1 will be modified to account for differences in measuring the response of clinically evaluable brain lesions as opposed to systemic lesions (modified RECIST, or mRECIST). Size is considered the tumor's largest diameter. Measurements from multiple lesions are summed to calculate the sum of the diameters (SD). The SD calculated on a baseline scan performed within 28 days of study drug initiation will be used as a reference to determine the objective response of the clinically evaluable lesions. All responses must be confirmed at 4 weeks with an equivalent or better response. Please refer to the original RECIST criteria if further

reference is necessary. Please see section 5.2 for response assessment in patients requiring local therapy while on study.

### **Measurable disease**

Specification of a minimal lesion diameter for measurable lesions reduces the potential for variation in the measurement of smaller lesions due to slice selection and volume averaging. The minimal lesion diameter should be greater than or equal to 2 times the section thickness and a minimum of 5mm. A previously irradiated lesion will not be measured as a target lesion unless it is documented to have progressed since treatment.

### **Nonmeasurable disease**

Nonmeasurable lesions at baseline are important in clinical trials because tumor progression may occur at these sites. Nonmeasurable lesions include enhancing lesions that are less than the specified smallest measurable diameter (5mm when slice thickness is 2.5mm or twice the slice thickness), hemorrhagic or predominantly cystic or necrotic lesions that are difficult to accurately measure and track, and lesions that are indeterminate for metastatic disease. Intrinsic T1-hyperintensity is noted within hemorrhagic lesions that may be misinterpreted as enhancing tumor, and for this reason, the precontrast T1-weighted image must be examined at baseline to prevent this error. Nonmeasurable lesions should be briefly described on the imaging case report form for each study.

RECIST 1.1 limits the number of lesions measured to 5 in total, with 2 per organ. For our purposes, even if there are multiple measurable lesions in the brain, the sum of diameters of up to a maximum of 5 of the largest lesions will be considered for response assessment.

### **Modified response criteria for brain metastases**

Complete Response (CR): Disappearance of all target lesions.

Partial Response (PR): At least a 30% decrease in the sum of diameters of target lesions, taking as reference the baseline sum diameters.

Progressive Disease (PD): At least a 20% increase in the sum of diameters of target lesions, taking as reference the smallest sum recorded since the treatment started or the appearance of one or more new lesions (new lesions must be greater than slice thickness).

Stable Disease (SD): Neither sufficient shrinkage to qualify for PR nor sufficient increase to qualify for PD, taking as reference the smallest sum diameters since the treatment started.

Please refer to RECIST v1.1 for additional details regarding response criteria.

## **10.2 Systemic Disease Response Assessment**

Response of all systemic, non-cerebral metastases will be evaluated in this study using the new international criteria proposed by the Response Evaluation Criteria in Solid Tumors (RECIST)

Committee v1.1. Version 1.1 stipulates that the number of lesions required to assess tumor burden for response determination has been reduced to a maximum of five total lesions (two lesions maximum per organ).

Briefly, measurable lesions must have a minimum size of 10 mm by CT scan (CT scan slice thickness no greater than 5 mm) in at least one dimension. Lesions with a longest diameter of <10 mm are considered non measurable lesions and will be tracked as non-target disease. Tumor lesions in a previously irradiated area, or in an area subject to other loco-regional therapy, are not considered measurable unless there has been demonstrated progression in the lesion. For complete definitions of measurable and non-measurable disease, please refer to the RECIST v1.1 criteria.

### **10.3 Evaluation of Best Overall Response**

The Best Overall Response is the best response recorded from the start of the treatment until disease progression/recurrence (taking as reference for progressive disease the smallest measurements recorded since the treatment started). The patient's best response assignment will depend on the achievement of both measurement and confirmation criteria. The best response will take into consideration both the clinically evaluable brain metastases and systemic metastases, and therefore will include measurements from both mRECIST criteria (in the brain) and RECIST criteria (in the body) as follows:

Complete Response (CR): Disappearance of all target lesions in the brain and systemic disease.

Partial Response (PR): Partial response in both the brain and the systemic disease, or if there is PR at one site and SD at the other, the sum of diameters from the brain and systemic disease will be added and the best overall response will be considered PR if there is at least a 30% decrease, taking as reference the baseline sum diameters.

Progressive Disease (PD): Progressive disease in either the brain or the systemic disease will qualify as PD as the best overall response.

Stable Disease (SD): Stable disease in both the brain and systemic disease, or if the sum of diameters from the brain and systemic disease does not qualify for PR or PD (at least a 20% increase in the sum of diameters of target lesions), taking as reference the smallest sum diameters since the treatment started.

### **10.4 Duration of Response**

**Duration of overall response**: The duration of overall response is measured from the time that measurement criteria are met for CR or PR (whichever is first recorded) until the first date that recurrent or progressive disease is objectively documented (taking as reference for progressive disease the smallest measurements recorded since the treatment started).

The duration of overall CR is measured from the time measurement criteria are first met for CR until the first date that recurrent disease is objectively documented. Please note that objective documentation implies confirmation of response by imaging.

**Duration of stable disease:** Stable disease is measured from the start of the treatment until the criteria for progression are met, taking as reference the smallest measurements recorded since the treatment started.

### **10.5 Progression-Free Survival (PFS)**

PFS is defined as the time from initiation of study drug until the first documented, confirmed progression of clinically evaluable brain metastases based on mRECIST criteria, systemic disease based on RECIST criteria, or death. If there is progression of disease that is then confirmed on a follow up scan at least 4 weeks later, the initial date of documented progression should be used in the PFS analysis.

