#### 4.7 Duration of Therapy

In the absence of treatment delays due to adverse event(s), treatment may continue for up to 2 years or until one of the following criteria applies:

1	Disease progression (see Section 4.8)
2	Symptomatic deterioration of health status without objective evidence of disease progression. Every effort should be made to document objective progression of disease in such cases.
3	Imminent risk in the case of progressing lesion or new/worsening edema seen on brain MRI
4	Unmanageable toxicity most probably attributed to MK-3475 (see Table 2)
5	Development of intercurrent illness limiting the ability to comply with study or the development of uncontrolled concurrent illness that prevents further administration of treatment or confound the ability to interpret data
6	General or specific changes in the patient's condition rendering the patient unacceptable for further treatment in the judgment of the investigator
7	Patient request for discontinuation, patient withdrawal from study, or patient lost to follow up
8	Development of neurologic or systemic complications following local therapy to any lesion
9	Death
10	Study termination by sponsor

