#### 4.8 Treatment Beyond Disease Progression

If radiologic imaging shows PD, tumor assessment should be repeated >4 weeks later in order to confirm PD with the option of continuing treatment while awaiting radiologic confirmation of progression. If repeat imaging shows a reduction in tumor burden compared to the initial scan demonstrating PD, treatment may be continued as per treatment calendar. If repeat imaging confirms progressive disease, subject will be discontinued from study therapy. Patients may continue treatment with MK-3475 beyond PD by RECIST 1.1 (in the body) or mRECIST in the brain, if they are determined by the investigator to be deriving clinical benefit from treatment and they continue to meet all other criteria for treatment. Patients who have rapid progression of disease or clinical deterioration will be removed from study. The decision to continue treatment beyond initial progression should be discussed with the medical monitor.

Additionally, in cases where the majority of the disease is stable or responding, and progressing lesions can be controlled with local therapy (ie resection or radiotherapy), the patient may be continued on trial following local therapy.

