### 5.2 Local Therapy

#### Local therapy for brain metastases:

Local surgical therapy in the form of craniotomy or LITT will be performed on the surgical lesion(s) prior to initiating systemic therapy. At any time point throughout the study, local therapy (surgery, gamma knife or LITT) will be administered to a lesion that becomes clinically concerning if deemed necessary by the investigators. This can be followed by continuation on MK-3475, provided that the patient is otherwise benefiting from therapy and has stable disease or disease shrinkage in other lesions by RECIST criteria. Approval from the study PI or co-PIs is required to continue treating the patient on MK-3475. A brain metastasis that has been treated locally will not be considered evaluable for response and will not be included when calculating the sum of largest dimensions. If the treated lesion constitutes  $> 25\%$  of the target lesions (for example, if one of three target lesions is treated locally), this will be considered progressive disease. If  $> 75\%$  of the baseline lesions are not treated with local therapy and evaluable by imaging, the patient will be considered evaluable, and response for the primary endpoint analysis will be assessed based on the remaining lesions. Additional response evaluation will be performed which will consider those patients who require local therapy while on study as having PD at the time of local therapy.

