**11.3 Analytic Plan for Secondary Objectives:**

- (1) Best overall response rate (ORR) is defined as the percentage of patients who experience a CR or PR in any metastases (clinically evaluable cerebral or systemic) as determined by mRECIST criteria in the brain or RECIST criteria in the body. The proportion of patients

with an ORR will be calculated with a 95% confidence interval. A similar analysis will be performed using ir-mRECIST and ir-RECIST.

- (2) B7-H1 (PD-L1) expression and other potential biomarkers will be correlated to clinical endpoints. Exploratory, hypothesis-generating analyses will be performed.
- (3) Progression-free survival will be calculated as the time from start of MK-3475 to progression (using mRECIST criteria for brain lesions and RECIST criteria for systemic disease) or death. Overall survival will be calculated as the time from start of MK-3475 to death. Patients who do not meet the endpoint will be censored at the date of last follow-up. PFS and OS will be determined separate for each arm and median survival will be estimated by using Kaplan-Meier methodology
- (4) Safety and toxicity will be assessed using CTC v4.0 criteria. All participants who receive any amount of study drug will be evaluable for toxicity.

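### Section 10.5 counts only confirmed progression towards PFS and has no rule for progression that is never re-scanned; Section 11.3(3) leaves confirmation out and should be aligned with it

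*Combined protocol and SAP*

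**What the plan says.** The protocol's measurement chapter, Section 10.5, defines the endpoint: "PFS is defined as the time from initiation of study drug until the first documented, confirmed progression of clinically evaluable brain metastases", with systemic progression by RECIST and death as the other events. It back-dates a progression confirmed at least 4 weeks later to the scan that first showed it. It does not mention a progression with no second scan.

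The analytic plan, Section 11.3(3), reads: "Progression-free survival will be calculated as the time from start of MK-3475 to progression (using mRECIST criteria for brain lesions", with RECIST for systemic disease, or death. Confirmation is not mentioned. It adds: "Patients who do not meet the endpoint will be censored at the date of last follow-up".

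Other sections bear on whether a confirming scan exists:

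- Section 4.8 asks for a repeat assessment after radiologic progression, and "If repeat imaging shows a reduction in tumor burden compared to the initial scan demonstrating PD, treatment may be continued". It also says "Patients who have rapid progression of disease or clinical deterioration will be removed from study".
- Section 4.7, on symptomatic deterioration, says "Every effort should be made to document objective progression of disease in such cases".
- Section 5.2 calls progression when locally treated lesions exceed 25% of the target lesions. It also says "A brain metastasis that has been treated locally will not be considered evaluable for response and will not be included when calculating the sum". An additional response evaluation "will consider those patients who require local therapy while on study as having PD at the time of local therapy".
- Section 6.3 continues scans after treatment ends, but only to progression or new anti-cancer therapy, among other stops. Survival contacts go on after that.

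**The concern.** A confirmation requirement is sensible for an immunotherapy, because lesions can enlarge and then shrink. It needs a companion rule for progressions that nobody re-images, and Section 10.5 has none. Applied literally, the patient has no event on the day progression was seen. He or she stays in the PFS analysis as progression-free until death or until the last contact.

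The patients affected are not a random subset. They include those removed for rapid progression or deterioration and those sent to local brain therapy. Section 1 lists median PFS among the measures of efficacy. The arms have no control, so PFS can only be read against outside figures, and a definition that lengthens it affects that reading directly.

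**Working it through.** **1. Is a confirming scan assured?** The mRECIST criterion for progression in Section 10.1 has no confirmation element. The general confirmation rule that opens Section 10 covers responses only.

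| Route | Place | Confirming scan |
|---|---|---|
| Rapid progression or deterioration, removed from study | 4.8 | Requested in general, not assured |
| Brain progression, off study for local therapy | 4.1 | Not assured; the lesion may be treated first |
| Progression first seen after treatment ends | 6.3 | Scheduled imaging stops at progression |
| More than 25% of target lesions treated locally | 5.2 | Treated lesion leaves the sum, so re-measuring it cannot confirm |

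**2. Effect on one patient.** Let P be the scan showing progression, D death and C last follow-up. Counting first progression gives an event at P. Confirmed-only with no second scan gives time min(D, C), with an event only if D ≤ C. Since D and C are not before P, that patient's time never gets shorter, so expected PFS goes up where the progression is real. The Kaplan-Meier estimate in a single small arm need not rise, because a later event falls on a smaller risk set.

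**3. Size.** The plan gives no PFS target, event count or power, so there is no figure to reproduce. All inputs below except the scan interval are assumptions:

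- Time to progression is exponential with median 2 or 4 months. Section 2.5 cites medians up to 4 months for NSCLC chemotherapy trials.
- Survival after progression has median 4 months, or 1 month in the unconfirmed group.
- Scans fall every 8 weeks (56/30.44 = 1.84 months). The week-4 MRI is left out because calendar footnote G makes it safety-only.
- A share f of progressions is never confirmed.

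Median PFS in months, counting first progression → confirmed-only:

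| Time to progression / survival of unconfirmed group | f = 20% | f = 30% | f = 50% |
|---|---|---|---|
| 2 / 4 | 3.4 → 3.68 (+0.3) | 3.4 → 3.68 (+0.3) | 3.4 → 4.31 (+0.9) |
| 4 / 4 | 5.52 → 5.52 (0) | 5.52 → 5.52 (0) | 5.52 → 7.36 (+1.8) |
| 2 / 1 | 3.06 → 3.45 (+0.4) | 2.97 → 3.48 (+0.5) | 2.82 → 3.51 (+0.7) |
| 4 / 1 | 5.43 → 5.52 (+0.1) | 5.31 → 5.52 (+0.2) | 5.10 → 5.52 (+0.4) |

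A separate simulation added deaths without progression (median 24 months) and follow-up of 6 to 36 months. With 4 months to progression and 6 months' survival after it, the median for 44 patients went from 3.7 to 5.0, 5.5 and 7.1 months at 10%, 25% and 50% unconfirmed. For 20 patients it went from 3.7 to 3.7, 5.3 and 6.2. Across all its settings (2 or 4 months; survival 3, 6 or 12 months) the rise was 0 to about 3.7 months.

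The two models differ because the median tends to sit on a scan date and jumps by an interval. With 4 months to progression, 0.5^(3.68/4) = 52.9% are progression-free after week 16, so the median passes to the next scan. Deaths without progression multiply this by 0.5^(3.68/24) = 0.899, giving 47.5%, and the median is then 3.68.

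**4. Direction in single arms** (20 or 44 patients, 2 months to progression, f = 20% or 50%). The estimated median rose in 25–92% of arms, was unchanged in 9–75% and fell in at most 0.4%. In the separate simulation it was equal or longer in at least 99.8% of replicates.

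**5. The opposite error.** If 11.3(3) were read literally, a progression that shrinks on re-scan would still be an event. In the 2/4 setting, with 5% or 10% of patients event-free at week 8 affected, 6-month PFS is 13.9% or 13.2% against 14.7%.

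**6. Censoring date alone.** With 10%, 20% or 30% leaving imaging at week 8, 6-month PFS is 17.1%, 19.5% or 22.0% (last follow-up) against 16.9%, 19.2% or 21.6% (last scan). The differences are 0.2, 0.3 and 0.4 points.

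**The case against.** Section 10.5 carries the PFS title, gives the definition and tells the analyst which date to use. Section 11.3(3) has the same start, criteria and death component and omits only confirmation. A reader might infer two rival endpoints with no way to choose between them. The documents do not support that: 11.3(3) is most naturally a shorter restatement. This stands, and on that reading the opposite error in step 5 largely falls away. It does not supply the missing rule in 10.5.

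Confirmation is also partly provided for. Section 4.8 asks for a re-scan and 4.7 for every effort to document progression. The imaging stop in 6.3 could be taken to mean confirmed progression, which would close that route. Patients with unconfirmed progression who die still count, at death. These points shrink the gap without closing it.

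On size, a reader might point to 6-month PFS, which in the 2/4 setting goes from 15% to 23%, 28% or 36%. The plan specifies median PFS and never a 6-month rate. With 1-month survival in the unconfirmed group the rise is only 2 to 5 points, and the estimated 6-month rate fell in up to 25% of simulated arms. The 50% share has no basis in the documents. Sampling error is also large. Assuming exponential times and an event for every patient, 3.4 × exp(±1.96/√n) gives 2.2 to 5.3 months for 20 patients and 2.5 to 4.6 for 44.

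**Conclusion.** The gap is real and should be closed. Section 10.5 as written, with censoring at last follow-up, moves a real but never re-scanned progression to death or to a later censoring date, so PFS is expected to be overstated.

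The size cannot be fixed from the documents, which give no share of unconfirmed progressions. It is nil if all are confirmed. With 4-month survival after progression, the planned median moves by 0 to less than 0.4 months at 20–30% unconfirmed, and by more at 50%. The separate model shows a full scan interval is possible at 25%.

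A reader might infer that reported PFS is bound to be inflated. That goes too far: direction holds in expectation, not for every arm, and it does not apply to lesions that shrink on re-scan, where 10.5 gives the sensible answer. Nor does the point reach the trial's main conclusion. PFS is secondary and estimation-only; BMRR, sample size and monitoring bounds do not use it. The censoring date is a small separate matter.

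**What to change.** Put one definition in both 10.5 and 11.3(3):

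- The event is the first documented progression (mRECIST in the brain, RECIST in the body) or death.
- A progression is set aside only if a scan at least 4 weeks later does not confirm it. That scan must precede any local therapy to the progressing lesions and any new anti-cancer therapy. Without this condition, treating a lesion could erase a real progression.
- A progression with no such scan counts on its first date.
- Progression under the 25% target-lesion rule in 5.2 is dated at the local therapy. The broader evaluation that treats any local therapy as progression stays an additional analysis.
- PFS is censored at the last adequate tumour assessment; last follow-up is kept for OS only.
- Confirmed-only PFS is reported as a sensitivity analysis.

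The re-scan interval is worded as more than 4 weeks in 4.8 and at least 4 weeks in 10.5; these should be reconciled.

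The cost is a few sentences, using scan and therapy dates already collected. Reported PFS may be slightly less favourable. No treatment rule, sample size or monitoring bound changes.

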#### Local therapy for extra-cerebral metastases:

Local surgery or radiation therapy (if indicated for palliative measures only after discussion with the study PI or co-PIs) may be permitted and the patient can continue to receive MK-3475 provided there is otherwise evidence of clinical benefit from treatment (i.e. stable disease or response in measurable lesions). The criteria applied for assessing brain metastasis response will be applied to extra-cerebral metastases as well.

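### PFS is defined two ways (confirmed progression in 10.5, any progression in 11.3), and neither says how to count a progression given local therapy before its confirmation scan

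*Combined protocol and SAP*

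**What the plan says.** **PFS event.** Section 10.5 counts time from first dose "until the first documented, confirmed progression of clinically evaluable brain metastases based on mRECIST criteria", confirmed systemic progression by RECIST, or death. When a scan at least 4 weeks later confirms the progression, "the initial date of documented progression should be used in the PFS analysis". It gives no rule for a progression that is never confirmed.

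**PFS analysis.** Section 11.3(3) reads differently: "Progression-free survival will be calculated as the time from start of MK-3475 to progression (using mRECIST criteria for brain lesions" and RECIST for the body, or to death. Confirmation is not mentioned. "Patients who do not meet the endpoint will be censored at the date of last follow-up"; local therapy is not addressed.

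**Local therapy on study.** Section 4.8 deals with patients whose tumour burden is mostly stable or shrinking: if "progressing lesions can be controlled with local therapy (ie resection or radiotherapy), the patient may be continued on trial following local therapy". Section 5.2 likewise permits continued MK-3475 after local therapy to a brain lesion, with approval from a study PI. Neither section makes local therapy wait for the confirmation scan.

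**Effect on measurement.** Under 5.2 a locally treated brain metastasis is not evaluable and "will not be included when calculating the sum of largest dimensions". If more than 25% of the target lesions are treated, "this will be considered progressive disease"; the section's own example is one target of three. It also plans an additional response evaluation that scores any on-study local therapy as PD at that time. For the body, "The criteria applied for assessing brain metastasis response will be applied to extra-cerebral metastases as well".

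**The concern.** The lesion that caused the progression can be gone from the sum by the time of the scan meant to confirm it. If no other disease progresses, 10.5 has nothing to confirm. The patient's PFS then runs on to a later progression, to death, or to censoring at last follow-up, so the error can only lengthen PFS. The affected patients matter in a trial of CNS activity, because their lesions grew enough to prompt surgery or radiation. PFS that passes over them mixes control by MK-3475 with control by local treatment.

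Sections 10.5 and 11.3(3) also give different answers for these patients. With both in force, the analyst could choose between them after seeing the data.

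**Working it through.** The documents give no PFS sample size, event count, power or expected median, so there is no PFS figure to reproduce. Three checks follow.

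**1. Which treated lesions does the >25% rule in 5.2 reach?** Section 10.1 allows at most 5 brain targets. The share is treated targets divided by all targets.

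| Targets | One treated | PD by the >25% rule? | Two treated | PD by the >25% rule? |
|---|---|---|---|---|
| 1 | 100% | yes | – | – |
| 2 | 50% | yes | 100% | yes |
| 3 | 33.3% | yes | 66.7% | yes |
| 4 | 25.0% | no | 50% | yes |
| 5 | 20.0% | no | 40% | yes |

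The target-lesion gap is therefore one treated lesion of 4 or 5. A new lesion is PD under 10.1 but is not a target, so the rule does not reach it whatever the number of targets.

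**2. Can the repeat scan confirm the progression from the sum?** PD needs an increase of at least 20% over the smallest sum (10.1). Take equal 10 mm targets with one growing and the others unchanged.

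- Five targets: one grows from 10 to 20 mm. The sum goes from 50 to 60 mm, 60/50 − 1 = +20%, which is PD. After treatment 40 mm remain: 0% against the same four lesions, or 40/50 − 1 = −20% against the old sum. It is not confirmed, and 20% is not above 25%.
- Four targets: one grows from 10 to 18 mm. The sum goes from 40 to 48 mm, +20%, PD. After treatment 30 mm remain: 0%, or −25% against the old sum. It is not confirmed, and 25% is not above 25%.
- Three targets: one grows from 10 to 16 mm. The sum goes from 30 to 36 mm, +20%, PD. After treatment 20 mm remain: 0%, or −33.3%. The sum does not confirm it, but 33.3% exceeds 25%, so 5.2 assigns PD.

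The result is the same whether or not the reference sum is recalculated without the treated lesion. For the three-target patient, no section says whether the assigned PD is a PFS event, whether it needs confirmation, or what date it takes.

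**3. How far could the median move?** Assumptions, none from the documents: time to first progression is exponential with hazard λ; a share f of first progressions is skipped; a skipped patient's next counted event follows after a further exponential time with the same hazard. Then

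S(t) = (1 − f)·exp(−λt) + f·exp(−λt)(1 + λt) = exp(−λt)(1 + fλt).

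Solving S(t) = 0.5 and dividing by the true median, ln 2/λ, gives a ratio that does not depend on λ. The last column lets the later hazard range from twice to half the original.

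| f | Ratio, same hazard | Ratio, hazard ×2 to ×0.5 |
|---|---|---|
| 5% | 1.05 | 1.04–1.06 |
| 10% | 1.11 | 1.07–1.13 |
| 20% | 1.23 | 1.15–1.30 |
| 30% | 1.36 | 1.23–1.49 |

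**The case against.** A reader might infer that the plan's PFS skips every progression treated locally before confirmation and is therefore overstated. The documents do not support that, for four reasons.

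- Section 11.3(3) requires no confirmation. If it governs, the first PD is the event and nothing is skipped. The upward bias belongs to 10.5 only.
- For patients with 1 to 3 targets, treating any target is PD under 5.2, and so is treating two or more of 4 or 5. Nothing says this PD is excluded from PFS. One can argue that an assigned PD is not a scan result and so cannot be confirmed, but that is an inference; the text is silent.
- Progression can still be confirmed if untreated brain lesions or systemic disease progress at the repeat scan. Section 4.8 opens this route where most disease is stable or responding, which makes that less likely but not impossible.
- The share f is unknown. It is limited by the conditions on continuing treatment and by the cases that 5.2 already calls PD.

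These points stand, and they narrow the concern. They do not remove it. For one treated lesion of 4 or 5 targets, and for a treated new lesion, nothing rescues the event under 10.5 unless other disease progresses. The additional evaluation in 5.2 would count these patients, but it is described as a response evaluation, and 10.1 refers to 5.2 only for response assessment.

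**Conclusion.** The concern holds in this limited form. Sections 10.5 and 11.3(3) conflict on confirmation. Under 10.5 a real progression can go uncounted when its lesion is treated before the repeat scan, and the direction of any resulting bias is toward longer PFS. With 1 to 3 targets the outcome is undefined rather than wrong.

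The size cannot be derived from the documents. The 11–36% lengthening of the median for f between 10% and 30% rests on exponential times, an unchanged later hazard and an assumed f; halving or doubling the later hazard widens the range to 7–49%. These figures illustrate sensitivity and do not estimate the bias in this trial.

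PFS is a secondary endpoint, estimated by Kaplan-Meier within each arm with no planned test. The sizing and decision rules for the brain metastasis response rate are unaffected. The wording should be corrected, but the point does not threaten the primary result.

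**What to change.** Use one PFS definition in 10.5 and 11.3(3), and add to both:

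> Progression by mRECIST or RECIST 1.1 followed by local therapy to the progressing lesion before the confirmation scan is a PFS event on the date of the scan that first showed progression, without confirmation. If PD is assigned under section 5.2 with no earlier scan showing PD, the PFS event date is the date of local therapy.

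The condition in the second sentence keeps the two rules from giving one patient two dates. Report PFS under the confirmed-only rule as a labelled sensitivity analysis, so that readers can see how much the choice matters.

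The cost is a few sentences of wording, with no new data and no change to patient care. The downside is that median PFS may be shorter, and some unconfirmed progressions, possibly pseudoprogression, will count as events.
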